6.1.4 Adjustments for Covariates

Analysis of covariance will include baseline value as a covariate.

6.1.5 Handling of Dropouts or Missing Data

Should a determination of treatment period (on treatment, pre-treatment, post-treatment) be required for AEs or concomitant medication but the corresponding date is missing, or is a partial date, the event/medication will be considered on treatment unless the portions of the date that are available indicate this is not possible.

The primary method of handling missing efficacy data will be Markov Chain Monte Carlo (MCMC) multiple imputation. Imputation will be conducted within each treatment group independently, so the pattern of missing observations in one treatment group cannot influence missing value estimations in another. For each imputation process, 25 imputations will be performed.

Subjects that withdrew from the study due to lack of efficacy will have missing values imputed, however, the WI-NRS responder status will be defined as non-responder. Subjects that used an excluded therapy to treat worsening of pruritus or PN will have data values collected after the use of the excluded therapy set to missing and subsequently imputed. These subjects will also have the WI-NRS responder status defined as non-responder.

Missing WI-NRS data will be derived for the analysis using the method of MCMC multiple imputation. The 4-point responder status will be derived from imputed WI-NRS values. Since both primary and key secondary endpoints require WI-NRS, the following steps will be followed:

1. Using the daily eDiary data, calculate Baseline and Week 1 through Week 10 values by averaging available values. In order to compute a week's average, a minimum of 4 values must be available for that week. The weekly average will be imputed when there are fewer than 4 values available.
2. From step 1, create a dataset for each treatment group, of subjects with observed values and those needing estimation by MCMC. The missing WI-NRS values in each dataset will be filled in using the MCMC method to generate 25 datasets. The resulting datasets for each treatment group will be combined into one complete dataset.

Syntax:

```
proc mi data=datain out=dataout seed=&seed. Nimpute=25 <options>;
  where trtpn=(TRT); /* Note TRT = [1, 2]; depending on treatment group */;
  mcmc chain=single;
  var baseline week1 week2 week3 week4 week5 week6 week7 week8 week9
      week10;
run;
```

3. From each complete dataset, the dichotomous responder rate will be determined. Each complete dataset will be analyzed as specified for the particular analysis.

The results from the analyses will be combined into a single inference using SAS® PROC MIANALYZE. In the case of the primary analysis and the secondary responder analyses, the Cochran Mantel Haenszel (CMH) statistics computed in the analyses of WI-NRS responder rates will be normalized using the Wilson-Hilferty transformation prior to combining them using SAS® PROC MIANALYZE.

A total of 2 random seeds will be needed to impute missing data. Those random seeds have been pre-specified by using a random number generator:

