Early termination of a subject from the study may occur due to loss to follow-up or withdrawal of consent by the subject. In accordance with legal requirements and International Conference on Harmonization (ICH) –GCP guidelines, every subject or his/her legal representative has the right to withdraw from the study at any time and without providing reasons. If provided, the reason (adverse event, study burden, lack of efficacy, other) a subject withdrew consent will be recorded in the electronic Case Report Form (eCRF). The PI or site staff must make every effort to contact subjects who are suspected of being lost to follow-up. Attempts to contact such subjects must be documented in the subject's source documents.

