Pregnancy in a female clinical trial subject or female partner of a male clinical trial subject is not an SAE per se. Complications of such pregnancies (for example, spontaneous abortion) may qualify as SAEs and should be reported as such even if they occur after the Follow-up visit. Any congenital anomalies/birth defects must be recorded and reported as SAEs. See Safety Form Completion Instructions for complete instructions.

7.1.6 *Worsening of Pruritus or PN*

Pruritus or PN should be recorded as an AE or SAE only if considered by the investigator to have worsened in severity beyond the subject's typical fluctuations. It is important to include a description of the nature of the unexpected worsening when recording the AE or SAE (e.g. new PN lesions in previously uninvolved skin).

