8.2 Handling of Missing Data

Should a determination of treatment period (on treatment, pre-treatment, follow-up) be required for adverse events or concomitant medication but the corresponding date is missing, or is a partial date, the event/medication will be considered on treatment unless the portions of the date that are available indicate this is not possible.

The primary method of handling missing efficacy data will be MCMC multiple imputation. Subjects who withdrew from the study due to a lack of efficacy, or used an excluded therapy to treat worsening of pruritus or PN, will be defined as non-responder. Imputation will be conducted within each treatment group independently, so the pattern of missing observations in one treatment group cannot influence missing value estimations in another. For each imputation process, 25 imputations will be performed.

If a subject fails to complete their eDiary for the week prior to Week 10, the primary endpoint (WI-NRS) data will be missing, unless the subject withdrew from the study due to a lack of efficacy, or the subject used an excluded therapy to treat worsening of pruritus or PN, in which case their responder status will be defined as non-responder. If the Week 10 value is missing for any other reason, the change from baseline value will be based on imputed data. Missing Week 10 WI-NRS values from which the 4-point responder status is derived will be estimated by MCMC.

Missing WI-NRS data will be derived for the analysis using the method of MCMC multiple imputation. Since both primary and key secondary efficacy endpoints require WI-NRS, the following steps will be followed:

1. Using the daily eDiary data, calculate Baseline and Week 2 through Week 10 values by averaging available values. In order to compute a week's average, a minimum of 4 values must be available for that week. The weekly average will be imputed when there are fewer than 4 values available.
2. From step 1, create a dataset for each treatment group, of subjects with observed values and those needing estimation by MCMC. The missing WI-NRS values in each dataset will be filled in using the MCMC method to generate 25 datasets. The resulting datasets for each treatment arm will be combined into one complete dataset.

Syntax:

```
proc mi data=datain out=dataout seed=&seed. Nimpute=25 <options>;  
  where trtpn=(TRT); /* Note TRT = [1, 2]; depending on treatment group */;  
  mcmc chain=single;  

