6.7 Analysis of Efficacy

The efficacy endpoints will be summarized within the ITT and PP populations using descriptive statistics by time point and treatment. Available results including averaged imputed values, as well as change from baseline, will be summarized for each applicable time point. The WI-NRS and change from baseline will also be presented for each study day in a by-subject listing.

For the 4- and 3-point responder rate endpoints, subjects will be considered responders if they have at least a 4- / 3-point reduction between baseline and the corresponding week. Subjects that discontinued study drug due to lack of efficacy or used an excluded medication to treat worsening of pruritus or PN will be considered non-responders.

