Table 14.3.1.4.3.1.3: Summary of Reproductive Endocrine Laboratory Results (Safety Population – Females Not Using Hormonal Contraception/Therapy)104

Table 14.3.1.4.3.2: Shift Summary of Endocrine/Reproductive Endocrine Laboratory Results (Safety Population).....105

Table 14.3.1.5.1.1: Summary of Treatment-Emergent Electrocardiogram (ECG) Parameter Abnormalities (Safety Population).....106

Table 14.3.1.5.1.2: Summary of Electrocardiogram Parameters (Safety Population).....108

Table 14.3.1.5.1.3: Shift Summary of Overall Electrocardiogram (ECG) Assessments (Safety Population).....109

Table 14.3.1.6.1: Summary of Vital Signs (Safety Population)111

Table 14.3.1.7.1: Summary of Hospital Anxiety and Depression Scale (HADS) (Safety Population).....112

Table 14.3.1.8.1: Summary of Epworth Sleepiness Scale (ESS) (Safety Population)113

Table 14.3.1.9: Summary of Pharmacokinetic Concentrations (Safety Population)114

Table 14.3.1.10: Summary of Menstrual Cycles (Safety Population)115

CONFIDENTIAL

Table 14.0.1: Summary of Subject Completion/Discontinuation
(Randomized Subjects)

	Placebo (N=xxx)	Serlopitant 5 mg (N=xxx)
Completed Treatment		
Yes	xx (xx.x%)	xx (xx.x%)
No	xx (xx.x%)	xx (xx.x%)
Reason for Discontinuation from Treatment		
Adverse Event	xx (xx.x%)	xx (xx.x%)
Lack of Efficacy	xx (xx.x%)	xx (xx.x%)
Pregnancy	xx (xx.x%)	xx (xx.x%)
Investigator Decision	xx (xx.x%)	xx (xx.x%)
Withdrawal by Subject from Treatment	xx (xx.x%)	xx (xx.x%)
Protocol Deviation	xx (xx.x%)	xx (xx.x%)
Sponsor Decision	xx (xx.x%)	xx (xx.x%)
Other	xx (xx.x%)	xx (xx.x%)
Completed Follow-up		
Yes	xx (xx.x%)	xx (xx.x%)
No	xx (xx.x%)	xx (xx.x%)
Reason for Discontinuation from Follow-up		
Withdrawal by Subject from Study	xx (xx.x%)	xx (xx.x%)
Lost to Follow-up	xx (xx.x%)	xx (xx.x%)
Other	xx (xx.x%)	xx (xx.x%)

SOURCE: USERNAME/SPONSOR/PROJECTJOBNAME (DATE,TIME)

Table 14.0.2: Summary of Subjects Excluded from Analyses
(Randomized Subjects)

	Placebo (N=xxx)	Serlopitant 5 mg (N=xxx)
Intent-to-Treat Population		
Number of Subjects Included	xx (xx.x%)	xx (xx.x%)
Number of Subjects Excluded	xx (xx.x%)	xx (xx.x%)
Reason for Exclusion		
Not Dispensed Study Drug	xx (xx.x%)	xx (xx.x%)
Safety Population		
Number of Subjects Included	xx (xx.x%)	xx (xx.x%)
Number of Subjects Excluded	xx (xx.x%)	xx (xx.x%)
Reason for Exclusion		
No Evidence of Subject Dosing	xx (xx.x%)	xx (xx.x%)
No Post-Baseline Assessment/TEAE	xx (xx.x%)	xx (xx.x%)
Per-Protocol Population		

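### A subject who leaves because itch or PN worsened may be coded as an adverse-event discontinuation, and unless an excluded therapy was used no rule then makes that subject a non-responder

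*SAP*

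**What the plan says.** Two events force non-response on the WI-NRS responder endpoints.

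- **Leaving for lack of efficacy.** SAP 6.1.5: "Subjects that withdrew from the study due to lack of efficacy will have missing values imputed, however, the WI-NRS responder status will be defined". The status assigned there is failure. SAP 6.7 applies the rule to a different event, stopping drug: "Subjects that discontinued study drug due to lack of efficacy or used an excluded medication to treat worsening of pruritus or PN" are scored as failures.
- **Rescue for worsening.** SAP 6.1.5: "Subjects that used an excluded therapy to treat worsening of pruritus or PN will have data values" after that use set to missing and imputed, with responder status fixed as failure.

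For everything else, Protocol 8.2 (version 4.0) says: "If the Week 10 value is missing for any other reason, the change from baseline value will be based on imputed data". The imputation runs separately in each arm and uses only baseline and Weeks 1 to 10 WI-NRS. The reason for leaving and any adverse event are not in the model.

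On coding, Protocol 7.1.6 says: "Pruritus or PN should be recorded as an AE or SAE only if considered by the investigator to have worsened in severity". The yardstick given is that person's usual variation. Protocol 6.5.11 lists the withdrawal reasons: "If provided, the reason (adverse event, study burden, lack of efficacy, other) a subject withdrew consent will be recorded" in the case report form. SAP Table 14.0.1 has separate rows for Adverse Event and Lack of Efficacy under "Reason for Discontinuation from Treatment". Neither appears under discontinuation from follow-up.

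**The concern.** The plan treats leaving for inadequate itch control as failure, and treats worsening as failure when the subject takes an excluded therapy. It does not cover the subject who worsens, takes no excluded therapy and leaves. Protocol 5.7.3 strongly discourages rescue, so that path is foreseeable. Scoring then depends on which of two overlapping codes the site picks. Coded lack of efficacy, the subject is always a failure. Coded adverse event with Week 10 missing, the subject is a responder in some of the 25 imputed datasets.

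Because imputation is within arm, the same clinical course has a better chance of being scored a response in the arm that responds better. The rule governs the primary endpoint and both key secondary endpoints.

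**Working it through.** The documents give no figure for this effect, so there is none to reproduce. The stated power of more than 90% cannot be rechecked because its assumed rates are blacked out, and nothing below depends on it.

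**1. The coding path.** Protocol 7.1.6 permits worsened itch or PN to be logged as an adverse event. Protocol 6.5.11 and Table 14.0.1 offer adverse event as a reason distinct from lack of efficacy. Protocol 8.2 then imputes. Each step follows the plan as written, so the gap needs no deviation to occur.

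**2. Who lacks a Week 10 value.** SAP 6.1.3 defines Week 10 as Days 64 to 70 and requires four entries, so the diary must run to at least Day 67. Under Protocol 5.6 and 6.5.10 an early stopper has Follow-up 35 (+7) days after last dose. Table 3 has the diary running until then. Assuming daily entries and visits in window:

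- Last dose Day 24: 24 + 42 = Day 66, three entries at most, so Week 10 is missing.
- Last dose Day 32: 32 + 35 = Day 67, four entries, so Week 10 can be observed.
- Days 25 to 31 depend on where the visit falls in its window.

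Table 2 also marks diary collection at early treatment discontinuation. If that is followed, later stoppers lose Week 10 too.

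**3. Chance that a worsened leaver is imputed a response.** The documents give no SD or correlation, so these are assumptions: SD of change 2.0 to 3.0; correlation r of the last observed week with Week 10 of 0.3 to 0.9; leaver c = 0.5 to 1.0 points above baseline; arm mean change at the last observed week equal to f = 50% to 100% of the Week 10 mean change. Arm means m are set to reproduce the Phase 2 PN study's 4-point responder rates, 25.0% placebo and 54.4% serlopitant (average VAS, Week 8, post hoc; Protocol 1.5.3).

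P = Φ{[−4 − m − r(c − f·m)] / [SD·√(1 − r²)]}

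Example with SD 2.5, r = 0.7, c = 0.5, f = 0.5, where the denominator is 2.5 × 0.714 = 1.785:

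- Placebo, m = −2.31: conditional mean −2.31 + 0.7 × 1.655 = −1.15; z = −2.85/1.785 = −1.60; P = 5.5%.
- Serlopitant, m = −4.28: conditional mean −4.28 + 0.7 × 2.64 = −2.43; z = −1.57/1.785 = −0.88; P = 19%.

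Over the whole grid P is 0 to 19% on placebo and 0 to 44% on serlopitant.

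A simulation of the within-arm imputation (140 per arm, 7 worsened leavers about 1 point above baseline, SD 2.5, between-week correlation parameter 0.5 or 0.8, 25 draws, four runs per setting) shows the dependence on timing:

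| Last diary week | Placebo | Serlopitant |
|---|---|---|
| 1 | 4–16% | 18–34% |
| 2 | 1–8% | 8–25% |
| 4 | 0–5% | 3–17% |
| 6 | 0–2% | 0–7% |

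**4. Effect on the treatment difference.** In the Phase 2 PN study 6 placebo and 3 serlopitant subjects discontinued for TEAEs. Denominators of 63 and 64 are inferred from the reported TEAE percentages (39/63 = 61.9%, 46/64 = 71.9%). Scaled to 140 per arm: 6/63 × 140 = 13.3 and 3/64 × 140 = 6.6. Treat all of them as worsening leavers with Week 10 missing:

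| Imputed response chance, placebo / serlopitant | False responders | Shift toward serlopitant |
|---|---|---|
| 2% / 8% | 0.27 / 0.53 | (0.53 − 0.27)/140 = 0.2 points |
| 5% / 20% | 0.67 / 1.31 | (1.31 − 0.67)/140 = 0.5 points |
| 10% / 35% | 1.33 / 2.30 | (2.30 − 1.33)/140 = 0.7 points |

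If instead 3% to 10% of each arm left this way, the shift runs from 4.2 × (0.08 − 0.02)/140 = 0.2 points to 14 × (0.35 − 0.10)/140 = 2.5 points.

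**The case against.** Several objections have force.

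- **The protocol does not require adverse-event coding.** A reader might infer from Protocol 7.1.6 that worsening leavers must be recorded as adverse-event withdrawals. That section governs whether an adverse event is logged, only beyond typical fluctuation, and says nothing about the discontinuation reason. The same subject could properly be coded lack of efficacy. This stands: the coding is permitted, not prescribed.
- **The rescue rule already catches part of the group.** Worsened subjects who used an excluded therapy are failures whatever their code. This stands and limits the gap to those who did not.
- **Stopping drug is not leaving the study.** Some stoppers can supply an observed Week 10. This stands for later stoppers if the diary is kept to Follow-up, but not for last doses up to Day 24, where false credit is also largest.
- **Imputation conditions on the subject's own high scores.** A reader might infer that the worst failures are commonly imputed as responders, or might apply whole-arm rates of 25% and 54%. Neither is supported: imputed response is a minority outcome in every setting examined.
- **Sensitivity analyses probe it.** LOCF carries a worsened score forward as non-response, and the tipping point analysis varies outcomes among missing subjects. Both help interpretation, but neither changes the primary p-value.

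**Conclusion.** The gap is real and narrow. A worsened leaver coded as an adverse event, without excluded therapy and without a Week 10 value, can be counted as a responder, while one coded lack of efficacy cannot.

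The size is about 0.2 to 0.7 percentage points toward serlopitant at Phase 2 discontinuation counts. That takes every TEAE discontinuation as itch or PN worsening, which the documents do not state, so it is an upper figure at those counts. It rises to at most 2.5 points if 10% of each arm left this way, and is near zero for late leavers.

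The direction is not fixed by the text. With Phase 2 counts it favours serlopitant only if the imputed chance there is more than 13.3/6.6, about twice, that on placebo. With equal response rates and equal leaving there is no shift. The documents therefore do not support a claim that this could decide the trial. It is a cheap correction to an ambiguous primary-endpoint rule.

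**What to change.** In SAP 6.1.5, 6.7 and 6.8.1, with matching text in Protocol 8.2 and 8.9.1, also define as non-responders those subjects whose treatment discontinuation or study withdrawal is attributed to an adverse event of worsening pruritus or PN. Identify them from the Primary AE Number already shown with the discontinuation reasons in Listings 16.2.1.1 and 16.2.1.2, using a preferred-term list fixed before unblinding. Their imputed-response chance then becomes zero in both arms.

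In the same edit, reconcile the trigger in SAP 6.1.5 (withdrawal from the study) with that in SAP 6.7 (discontinuation of drug), and say whether the rule overrides an observed Week 10 value. Table 14.0.1 records lack of efficacy only under treatment discontinuation, so the two triggers can pick out different subjects. Tables 2 and 3 of Protocol Appendix A should also be reconciled on when an early stopper returns the diary.

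The cost is a few sentences, a short blinded term list and a matching protocol edit. The listings already provide for the data. Responder rates may be marginally lower in both arms.

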6.1.6 Interim Analyses and Data Monitoring

No interim analyses will be performed.

6.1.7 Multicenter Studies

The clinical study will be conducted under a common protocol for each investigational site with the intention of pooling all data for analysis. Every effort will be made to promote consistency in study execution at each study site.

6.1.8 Multiple Comparisons/Multiplicity

The primary and key secondary endpoints will be analyzed. However, the statistical significance of the key secondary endpoints will only be considered should statistical significance be reached for the primary endpoint. Similarly, statistical significance within the key secondary endpoints will be considered based on a hierarchical approach, starting with the WI-NRS Week 4 responder rate followed by the WI-NRS Week 2 responder rate. If the first key secondary endpoint fails to reach statistical significance at a level of 0.05, then subsequent endpoints will not be considered statistically significant.

6.1.9 Examination of Subgroups

Descriptive summaries of the primary efficacy endpoint will be created for subgroups of the Intent-to-Treat (ITT) population. Subgroups include age (< median age; >= median age), sex, ethnicity, race and Baseline WI-NRS randomization strata.

6.2 Disposition of Subjects

An accounting of all randomized subjects by disposition will be presented. Subjects who discontinue study drug prematurely or withdraw from the study will be summarized and listed, with a description of the reason for early termination/withdrawal.

The number of subjects included in each population will be summarized. Subjects who are excluded from a population will be summarized by the reasons for exclusion.

6.3 Protocol Deviations

Protocol deviations leading to exclusion from an analysis population will be tabulated. Other protocol deviations will be presented in a data listing.

6.4 Data Sets Analyzed

The following analysis populations will be reviewed and approved by the Sponsor prior to unblinding the study.

6.4.1 Intent-to-Treat (ITT) Population

The primary efficacy population will be the ITT population, which will include all randomized subjects who were dispensed study drug. Subjects will be analyzed within the treatment group to which they are randomized.

6.4.2 Safety Population

The primary safety population will be all treated subjects with at least one post-baseline assessment or a reported TEAE. For safety analyses, subjects will be classified based upon treatment received. In the case that a subject received both treatments, subjects will be summarized within the serlopitant 5 mg group.

6.4.3 Per Protocol Population

Additional analyses performed on the Per Protocol (PP) population will be considered supportive. The PP population will include all subjects in the safety population who complete the Week 10 evaluations without any significant protocol deviations/violations (i.e., any subject or investigator activity that could have possibly interfered with the therapeutic administration of the treatment or the precise evaluation of treatment efficacy). The PP population will include subjects in the safety population who do not meet any of the following criteria:

- Violated the inclusion/exclusion criteria;
- Received a strong CYP3A4 inhibitor (See Appendix B in the Protocol);
- Received an excluded medication which may plausibly impact the primary endpoint at Week 10 (e.g. was provided to treat pruritus or PN);
- Have not been compliant with the dosing regimen (i.e. subjects must comply with 80-120% of the expected dosage of study medication during participation in the study);
- Have not completed Week 10 visit within ± 7 days window
- Have not completed the eDiary to provide the Week 10 WI-NRS Primary Endpoint

Subjects who discontinue from the study drug due to an adverse event related to study treatment or documented lack of treatment effect, or who met protocol-defined non-responder criteria, will be included in the PP population. Prior to breaking the blind other additional criteria may be added to the lists above to accommodate for unforeseen events that occurred during the conduct of the trial that result in noteworthy study protocol deviations.

Subjects will be analyzed within the treatment group to which they are randomized.

